3.8.2.6 Patient reported outcomes

The European Organization for Research and Treatment of Cancer’s core quality of life questionnaire (EORTC-QLQ-C30, version 3.0) and breast cancer specific questionnaire (EORTC QLQ-BR23, version 1.0) and the EuroQoL 5-level instrument (EQ-5D-5L, Version 4.0) will be used to evaluate patient-reported outcome measures of health-related quality-of-life, functioning, disease symptoms and treatment-related side effects.

The PRO instruments are planned to be administered during screening and every 8 weeks after randomization in the first 18 months, and every 12 weeks thereafter until the end of treatment. PRO assessments [redacted] will continue to be collected during the efficacy follow-up after the end of treatment.

The following time based intervals will be used to group the PRO data over time. Day is defined as date of PRO assessment date – randomization date + 1.

Table 3-6 Time windows for patient reported outcomes

	Time Interval
Baseline	Last assessment before or on date of randomization
Day 1 of Cycle 3, 5, 7, 9 until cycle 19	+/- 4 weeks centered around the planned assessment date (except for the first and last windows): i.e. days 2 to 85 for Cycle 3 Day 1 days 86 to 141 for Cycle 5 Day 1 days t-27 to t+28 for Cycle k Day 1 (k= 7, 9, ..., 17), where t=(k-1)*28+1 is the target day of the assessment day 478 to 547 for Cycle 19 Day 1
Day 1 of Cycle 22, 25, 28, ...	+/- 6 weeks centered around the planned assessment date: i.e. days 548 to 631 for Cycle 22 Day 1

	days 632 to 715 for Cycle 25 Day 1 days t-41 to t+42 for Cycle k Day 1 (k= 28, 31,...), where t=(k-1)*28+1 is the target day of the assessment
End of treatment	At the end of treatment visit
Efficacy follow-up	At each of the efficacy follow-up visits

If more than one assessment is done within the same time window, the assessment performed closest to the target date will be used. If 2 assessments within a time window are equidistant from the target date, then the assessment obtained prior to target date will be used.

The FAS will be used for all PRO summaries and listings.

EORTC-QLQ and EQ-5D-5L

The global health status/global QoL scale score of the EORTC QLQ-C30 is identified as a primary PRO variable of interest. The physical functioning, emotional functioning and social functioning sub-scale scores of the EORTC QLQ-C30, the breast cancer symptoms scale of the EORTC QLQ-BR23, and the visual analog scale (VAS) of the EQ-5D-5L are identified as secondary PRO variables of interest. High scores in the EORTC QLQ-C30 and QLQ-BR23 represent a higher response level. Thus a high score for a functional scale represents a high / healthy level of functioning; a high score for the global health status / QoL represents a high QoL, but a high score for a symptom scale / item represents a high level of symptomatology /problems. Higher scores in the EQ-5D-5L also correspond to better health states.

The number of patients completing QoL questionnaires and the number of patients missing/expected to have QoL assessments will be summarized by treatment arm for scheduled assessment time points (the number of ongoing patients will be used as denominator). Furthermore, the amount and the pattern of missing data may be explored by treatment arm and over time using summary statistics. The following categories will be used to describe whether the questionnaire was completed at a specific time point:

- yes, fully completed
- yes, partly completed
- no.

Scoring of raw data and methods for handling of missing items or missing assessments will be handled according to scoring manuals for each respective patient questionnaire ([Fayers et al 2001](#), [Rabin 2011](#)).

A time-to-event approach will be considered in the analysis of the time to definitive 10% deterioration in the primary and the secondary PRO variables of interest.

Definitive 10% deterioration is defined as a worsening in score by at least 10% compared to baseline, with no later improvement above this threshold observed during the treatment period, or death due to any cause. Time to deterioration is the number of days between the date of randomization and the date of the assessment at which deterioration is seen. If a patient has not had an event prior to analysis cut-off, end of treatment, start of new anti-neoplastic therapy, lost to follow-up, or withdrawal of consent, the time to deterioration will be censored at the date of

the last evaluation before the earliest of these times. Only assessments collected while the patient is on treatment and on or before the end of treatment visit will be included in the PRO time to deterioration analysis.

[figure not shown]
If deterioration is observed after two or more missing assessments, time to deterioration will be censored at the date of the last assessment prior to the deterioration. The rules for calculating number of missing assessments are the same as those for tumor assessments (see [Section 2.5.5](#))

Time to 10% deterioration in the global health status/QOL scale, and secondary PRO scales of interest as listed above, will be compared between the two treatment arms using a stratified log-rank test (strata based on IRT data) at one-sided 2.5% level of significance. The survival distributions will be presented descriptively using Kaplan-Meier curves. Summary statistics from the Kaplan-Meier distributions will be determined, including the median time to 10% deterioration and the proportions of patients without 10% deterioration at 2-monthly intervals. Both point estimates and 95% CIs will be presented. A stratified Cox regression model will be used to estimate the hazard ratio (HR) of time to deterioration, along with 95% confidence interval.

Change from baseline in all sub-scales obtained from EORTC QLQ-C30 and the breast symptoms score of QLQ-BR23, and the VAS of EQ-5D-5L will be analyzed using a linear mixed effects model for longitudinal data to assess the treatment effect over time including terms for treatment, stratification factors, time of visit (in weeks counting from the time of randomization to the time of a particular post baseline measurement), treatment by time of visit interaction, and baseline score. Time will be considered as a continuous variable in this analysis. The data for selected time points will also be fitted using a linear model including treatment stratification factors, and baseline value as covariates. The differences in least square means between treatment and control group, and the corresponding 2-sided 95% CI at selected time points will be presented.

For the mixed effects model, patients with baseline and at least one non-missing post-baseline assessments will be included. This analysis will only include assessments up to the time point where there are at least 50 patients on each of the treatments. Data collected under treatment (i.e. up to the EOT assessment) will be included. As a first approach, an unstructured correlation matrix will be used to model the correlation within patients. The structure of the correlation matrix will be investigated and simplified using likelihood ratio test if appropriate. If PRO is found not to follow a linear trend, the time variable might be considered as a categorical variable instead of continuous in the model.

Descriptive statistics (n, mean, median, SD, min, max) will be used to summarize the individual item and subscale scores from the EORTC QLQ-C30, QLQ-BR23, and EQ-5D-5L at each scheduled assessment time point. Additionally, change from baseline in the subscale scores at the time of each assessment will be summarized. Patients with an evaluable baseline score and at least one evaluable post baseline score during the treatment period will be included in the change from baseline analyses.

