### **10.5.2.5 ECOG performance status**

ECOG PS scale as described in [Table 7-3](#) will be used to assess physical health of patients. An analysis of time to definitive deterioration of the ECOG PS by one category of the score from baseline will be performed using the FAS. Deterioration is considered definitive if no improvement in ECOG PS is observed at a subsequent time of measurement during the treatment period following the time point where the deterioration is observed.

Patients that have not worsened at the data cut-off point will be censored at the date of last assessment prior to data cut-off. Kaplan-Meier method will be used to estimate the distribution of time to definitive worsening and median time to definitive worsening will be presented along with a 95% confidence interval. A stratified log-rank test at one-sided 2.5% level of significance will be used to compare the distribution of time to definitive worsening between the 2 treatment arms.

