#### **10.5.4 Patient-reported outcomes**

##### **Health-related quality of life questionnaires**

The EORTC QLQ-C30 questionnaire along with the disease-specific breast cancer module (EORTC QLQ-BR23) and the EQ-5D-5L will be used to assess patient's QoL data. The global health status/QoL scale score of the EORTC QLQ-C30 is identified as the primary patient-reported outcome variable of interest. Physical functioning, emotional functioning and social functioning scale scores of the EORTC QLQ-C30, the breast cancer symptoms scale score of the EORTC QLQ-BR23 and the visual analog scale of the EQ-5D-5L are identified as secondary patient-reported outcome variables of interest.

[figure not shown]
Scoring of raw QoL data and methods for handling of missing items or missing assessments will be handled according to scoring manuals for each respective patient questionnaire ([Fayers et al 2001](#), [Rabin 2011](#)). The number of patients completing each patient questionnaire and the number of missing or incomplete assessments will be summarized by each treatment group for each scheduled assessment time point for the EORTC QLQ-C30, EORTC QLQ-BR23 questionnaires, and EQ-5D-5L. No formal statistical tests will be performed on PRO data and hence no multiplicity adjustment will be applied. The FAS will be used for analyzing PRO data.

[figure not shown]
Descriptive statistics will be used to summarize the scored scales for the EORTC questionnaires and the EQ-5D-5L at each scheduled assessment time point. Additionally, change from baseline in the domain scores at the time of each assessment will be summarized. Patients with an evaluable baseline score and at least one evaluable post baseline score during the treatment period will be included in the change from baseline analyses.

[figure not shown]
The distribution of time to definitive 10% deterioration in the global health status/QoL from EORTC questionnaires will be assessed in the two treatment arms. The time to definitive 10% deterioration is defined as the time from the date of randomization to the date of event, which

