is defined as at least 10% relative to baseline worsening of the corresponding scale score (without further improvement above the threshold) or death due to any cause. If a patient has not had an event, time to deterioration will be censored at the date of the last adequate PRO evaluation. If a patient did not have any baseline PRO assessment, time to deterioration will be censored at the date of randomization. The distribution will be presented descriptively using Kaplan-Meier curves. Summary statistics from Kaplan-Meier distributions will be determined, including the median time to definitive 10% deterioration along with two-sided 95% CI. Additionally, time to definitive deterioration with different cutoff definitions (e.g. 5%, 15%) may be specified in the analysis plan as deemed appropriate. A stratified Cox regression will be used to estimate the hazard ratio, along with two-sided 95% CI. In addition, a longitudinal analysis will be performed to evaluate the two treatment groups with respect to changes in the global health status/QoL over time.

Similar survival and longitudinal analyses will be performed to evaluate the two treatment groups for physical functioning, emotional functioning and social functioning scale scores of the EORTC QLQ-C30 and the breast cancer symptoms scale score of the EORTC QLQ-BR23 as additional PRO analyses to facilitate the interpretation of these data.

[figure not shown]
[figure not shown]

[Redacted]

[Redacted]

[Redacted]

[Redacted]

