This document describes the detailed statistical methodology to be used for the Clinical Study Report (CSR) for the primary PFS analysis of study CLEE011E2301, a phase III, randomized, double-blind, placebo-controlled study of LEE011 (ribociclib) or placebo in combination with tamoxifen and goserelin or a non-steroidal aromatase inhibitor (NSAI) and goserelin for the treatment of premenopausal women with hormone receptor positive, HER2-negative, advanced breast cancer.

The content of this SAP is based on protocol amendment 4 (clee011e2301-v04--protocol). All decisions regarding final analysis, as defined in the SAP document, have been made prior to database lock and unblinding of the study data.

CSR deliverables (shells for tables, figures, listings) and further programming specifications are described in the Tables, Figures & Listings (TFL) shells and Programming Datasets Specifications (PDS), respectively.

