3.8.2 Secondary efficacy analyses

The secondary efficacy objectives in this study are to

- compare the two treatment arms with respect to overall survival
- evaluate the two treatment arms with respect to overall response rate and clinical benefit rate;
- describe time to response and duration of response in each treatment arm;
- evaluate the two treatment arms with respect to time to deterioration of ECOG Performance Status;
- evaluate patient reported outcomes for health-related quality of life in the two treatment arms.

OS is the key secondary endpoint. A hierarchical testing strategy, where OS is to be statistically evaluated and interpreted only if the primary efficacy endpoint PFS is statistically significant favoring the treatment arm, will be used to control the overall type-I error rate.

The analysis of all secondary efficacy endpoints will be performed based on the FAS.

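### The primary-analysis SAP plans formal log-rank tests on six patient-reported scales, which protocol 10.5.4 rules out and no multiplicity control covers

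*SAP*

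**What the plan says.** The SAP file holds two plans, one for the final study report and one for the primary PFS analysis. The final-report plan has no PRO analysis section, so this point concerns only the primary-analysis plan.

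Section 3.8.2.6 of that plan names one primary PRO variable (QLQ-C30 global health status/QoL) and five secondary ones: QLQ-C30 physical, emotional and social functioning, the QLQ-BR23 breast symptoms scale, and the EQ-5D-5L visual analogue scale (VAS). It states: "A time-to-event approach will be considered in the analysis of the time to definitive 10% deterioration in the primary and the secondary PRO" scales just listed. It then says that time to deterioration on these scales "will be compared between the two treatment arms using a stratified log-rank test (strata based on IRT data) at one-sided 2.5% level of significance". Kaplan-Meier summaries and a stratified Cox hazard ratio with 95% CI are planned alongside.

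Protocol section 10.5.4 states: "No formal statistical tests will be performed on PRO data and hence no multiplicity adjustment will be applied". For global health status/QoL it plans descriptive Kaplan-Meier curves and an estimate: "A stratified Cox regression will be used to estimate the hazard ratio, along with two-sided 95% CI". It then extends this: "Similar survival and longitudinal analyses will be performed to evaluate the two treatment groups for physical functioning, emotional functioning and social functioning scale scores", and to the BR23 symptoms scale. That sentence does not name the VAS, although 10.5.4 elsewhere lists the VAS as a secondary PRO variable of interest.

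Type I error control is described in SAP 3.8.2 and covers PFS and OS only: "A hierarchical testing strategy, where OS is to be statistically evaluated and interpreted only if the primary efficacy endpoint PFS is statistically significant".

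**The concern.** The protocol omits multiplicity adjustment for PROs because it plans no PRO tests. The SAP adds the tests but no adjustment, so the protocol's reason for having no adjustment no longer applies. A named test with a stated sidedness and significance level is a formal test on its face. Time to 10% deterioration in global health status/QoL is a listed secondary endpoint in both documents, so the result will be reported. A p-value below 2.5% on any of the six scales could then be presented as statistically significant, which the protocol excludes and no error control supports.

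**Working it through.** **No figure to reproduce.** Neither document gives a power, sample size or error rate for the PRO comparisons. The check is therefore a comparison of texts plus the error rate that the SAP's tests would carry.

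**Number of tests.** From SAP 3.8.2.6: 1 (global health/QoL) + 3 (physical, emotional, social functioning) + 1 (BR23 breast symptoms) + 1 (EQ-5D VAS) = 6. Without the VAS, the protocol's survival-analysis list gives 5.

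**Error rate under no PRO effect.** Each test uses one-sided α = 0.025.

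- Upper bound: k × 0.025.
- Independent tests: 1 − 0.975^k.
- Equally correlated normal statistics with correlation r: 1 − ∫ φ(z) Φ((1.96 − √r·z)/√(1 − r))^k dz.

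| Case | Six scales | Five scales |
|---|---|---|
| Upper bound | 0.150 | 0.125 |
| Independent | 0.1409 | 0.1189 |
| r = 0.3 | 0.1216 | 0.1051 |
| r = 0.5 | 0.1037 | 0.0915 |
| r = 0.7 | 0.0821 | 0.0742 |
| r = 0.9 | 0.0541 | 0.0508 |

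For the primary PRO scale alone the rate is 0.025. The values of r are assumptions.

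**Is this general practice for secondary endpoints here?** The SAP also tests ORR, CBR and ECOG performance status at one-sided 2.5% without adjustment. The protocol plans those tests in 10.5.2.1, 10.5.2.2 and 10.5.2.5; for ECOG it says: "A stratified log-rank test at one-sided 2.5% level of significance will be used to compare the distribution of time to definitive worsening". In the visible text, the PRO tests are the only ones the protocol rules out.

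**Is it loose wording?** Where the SAP wants description only, it says so. It rules out p-values for PFS from derived local assessments and for BIRC-based ORR, and rules out inferential comparison for time to response and duration of response. For PROs it calls the Kaplan-Meier curves descriptive but states the test in a separate sentence.

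**Is it a version effect?** The primary-analysis SAP says "The content of this SAP is based on protocol amendment 4", while the protocol supplied is amendment 7. The visible change lists for amendments 5, 6 and 7 show no edit to 10.5.4. The visible PRO entries in the SAP change log concern only the VAS wording and the repeated-measures analyses. Some lines in these lists are redacted.

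**Censoring (smaller point).** Protocol 10.5.4 counts death from any cause as an event and otherwise censors at the last adequate PRO evaluation. SAP 3.8.2.6 also includes death in the event definition. However, it censors at the last evaluation before the earliest of cut-off, end of treatment, new anti-neoplastic therapy, loss to follow-up or consent withdrawal, and uses only on-treatment assessments; SAP 2.4 repeats the new-therapy rule. A patient who had not deteriorated and dies after end of treatment is therefore not counted. The SAP also censors a deterioration seen after two or more missed assessments, which the protocol's PRO section does not mention. Protocol 10.5.1 expects 123 deaths at the primary PFS analysis. The documents do not say how many would follow end of treatment without prior deterioration, so no size or direction of bias can be given.

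**The case against.** The strongest reply is that the error rates above are hardly a consequence of the SAP's departure. The protocol itself plans hazard ratios with 95% CIs for five of the six scales, and unadjusted intervals would exclude 1 in favour of the test arm at about the same rates. The SAP adds only a p-value and a level. This stands: the fix removes the formal claim, not the chance that some scale looks favourable.

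Second, the upper bound and the independent figure are not realistic, because all six endpoints share patients, deaths and most censoring triggers. That is fair; the correlated rows are the relevant ones. Even at r = 0.9 the six-scale rate is about twice 2.5%.

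Third, one-sided 2.5% is also used for ORR, CBR and ECOG status outside the hierarchy, so the phrase alone does not mark an error-controlled claim. But the protocol provides for those tests and excludes the PRO ones.

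Fourth, the primary analysis took place in October 2017, PRO collection stopped with amendment 6, and later analyses are descriptive. Deleting the sentence would thus change no future analysis. This limits the remedy to labelling and documentation but does not remove the conflict.

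Fifth, redactions follow the protocol's scale list and affect the change logs, and the amendment 4 text is not available. The sentence listing the scales is itself complete, and nothing visible suggests that 10.5.4 changed.

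**Conclusion.** The point holds. SAP 3.8.2.6 plans six unadjusted tests at one-sided 2.5% that protocol 10.5.4 rules out. Read as formal tests with no true PRO effect, they carry a chance of at least one false positive between 5.4% and 12.2% for equal correlations of 0.9 down to 0.3, and never above 15%. Those correlations are assumed. Type I error for PFS and OS is not touched. The defect is a significance claim without protocol support, and it should be corrected. The VAS time-to-event analysis is an addition by the SAP. The censoring difference makes the SAP version an on-treatment analysis, with no bias claimed in either direction. The remaining uncertainty is the version gap and the redacted change-log lines.

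**What to change.** Remove the log-rank test and its significance level from SAP 3.8.2.6. Keep the Kaplan-Meier curves and the stratified hazard ratio with 95% CI as descriptive results, and mark the VAS analysis as added by the SAP. Where p-values have already been reported, label them nominal, draw no significance claim from them or from the unadjusted intervals, and document the departure from protocol 10.5.4.

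For censoring, label the SAP analysis as on-treatment and add one sensitivity run under the protocol's event and censoring rule, using whatever follow-up PROs and deaths were collected.

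The cost is one deleted sentence or a footnote, one label, and one further time-to-event run on existing data. No new data are needed.

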3.9 Safety evaluation

The assessment of safety will be based mainly on the frequency of adverse events and on the number of laboratory/ECG values that fall outside of pre-determined ranges. Other safety data (e.g. vital signs and special tests) will be considered as appropriate.

All safety outputs will use the safety set. The safety summary tables will include only 'on-treatment' events/assessments, i.e. those collected on or after the first date of study treatment and collected no later than 30 days after the date of last study treatment administration. The AEs started before the first dose but worsening during the treatment period are also considered as 'on-treatment' events. All safety events/assessments will be listed and those collected outside of the on-treatment window will be flagged.

3.9.1 Adverse events (AEs)

3.9.1.1 Coding of AEs

Adverse events are coded using the Medical Dictionary for Regulatory Activities (MedDRA) terminology.

